11.1 Analyses of Primary Outcomes

All-cause mortality comparisons will be based on a log-rank test stratified by disease severity and study site. The summary hazard ratio will be estimated using a Cox proportional hazards model stratified by disease severity and study site pharmacy, and the proportion of participants who died by fixed time points (e.g., Day 14 or 60) will be estimated using Kaplan-Meier estimates.

Time to sustained recovery comparisons will be based on Gray's test (rho=0) stratified by disease severity and study site [51]. Cumulative incidence functions for sustained recovery will be estimated by treatment group using the Aalen-Johansen estimator [52], and the recovery rate ratio (RRR) for sustained recovery will be estimated using the Fine-Gray method [53, 54], stratified by disease severity and study site pharmacy. Analyses for the sustained recovery outcome require methods that take into account the competing risk of death, as participants may die before ever achieving sustained recovery. The "sustained recovery" outcome requires knowledge of a participant's residence status for at least 14 days after arriving "home" (as defined in section 4.1.3); since all participants are hospitalized at study entry, it takes at least 15 days to attain this outcome. Gray's test compares the cumulative incidence functions for sustained recovery between the comparison groups, taking into account the competing risk of death. Gray's test with rho=0 is the analogue of the log-rank test in the presence of competing risks. The Aalen-Johansen estimator for cumulative incidence functions is the analogue of the

Version 1.0, 11th November 2022 US IND# 162149

Kaplan-Meier estimator in the presence of competing risks. The Fine-Gray method is the competing risks equivalent of Cox proportional hazards models; the RRR compares the cumulative incidence rates of sustained recovery between the study arms and is a sub-distribution hazards ratio. Importantly, these analyses do not censor deaths before recovery as is done in Kaplan-Meier and Cox proportional hazards; in contrast, the information that a participant died will be carried forward through the remainder of the trial, thus avoiding overestimation of the recovery rate. We will report all sub-hazard ratios (e.g., death and withdrawals/losses/missing data).

Clinical recovery scale comparisons will be based on a proportional odds models stratified by disease severity and study site. Summary adjusted odds ratios will be reported. A test for the proportional odds assumption across cumulative categories and stratification covariates will be performed by testing for separate slopes (a partial proportional odds model). In addition, cumulative probabilities of the ordinal outcome categories will be compared between treatment groups using logistic regression models.

To avoid loss of power when stratifying analyses by study site, unless specified otherwise, sites that contributed fewer than 20 participants to the analysis cohort will be pooled with other sites within the same geographic region, defined first by country and second by wider geographic organizational units, e.g., continent.

11.2 Analyses of Secondary and Safety Outcomes, and Subgroups

Secondary efficacy outcomes will be analyzed similarly to the primary outcome with an analogous structure. Time to discharge from initial hospitalization will be analyzed using a competing risks approach, similar to time to sustained recovery. Death in hospital is a competing risk to discharge. Days alive and home through the end of follow-up, EuroQol (EQ-5D-5L) and the 7 category ordinal outcome on Days 1-7, 14 and 28 will each be analyzed using proportional odds models, similar to the clinical recovery scale. These analyses will be stratified by disease severity and study site.

Effects on the primary efficacy and safety outcomes will be assessed for subgroups defined by baseline characteristics, including demographics, social determinants, duration of symptoms at enrollment, clinical history and presentation (including disease severity). Tests evaluating effect heterogeneity across subgroups will be carried out. Subgroup analyses will be interpreted with caution due to limited power and uncontrolled type I error. Unless specified otherwise, corrections for multiple testing will not be applied.

The clinical organ failure or serious infection (PDACE) safety outcome will be summarized and compared at various study days (e.g., Day 5, 14, 28 and 60) using Cochran Mantel Haenszel test stratified by study site and disease severity. Summaries and comparisons will be provided for each component of this composite as well, with comparisons being conducted when 5 or more events in that component have occurred. Time to event analyses will also be used to summarize the PDACE safety outcome. The other safety outcomes defined in Section 4.2.3 (composite of death, clinical organ failure or serious infection; the composite of cardiovascular events and thromboembolic events; and safety and tolerability outcomes) will be analyzed similarly.

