6.2.5 Stratification

Randomization will usually be stratified by study site pharmacy, and severity of disease at entry unless stated otherwise in the trial-specific appendix. Severity of disease is determined by the respiratory infection or syndrome being studied. For example, strata that define disease severity for COVID-19 are based on supplemental oxygen use at randomization such as 1) invasive mechanical ventilation (IMV) or extra corporal membrane oxygenation (ECMO), 2) high-flow nasal cannula (HFNC) or non-invasive ventilation (NIV), 3) less than HFNC/NIV.

Within each stratum, mass-weighted urn randomization will be used to generate the active and placebo assignments. This will ensure the desired treatment allocation ratio is maintained throughout the trial.

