6.4 Sample size and Statistical Considerations

For the endpoints considered, for any single trial, sample size will have to consider the target population (this may include the variant) and the treatment being studied (e.g., adherence).

This section provides illustrative sample size estimate examples for each of the three primary outcomes defined in section 4.1, under a range of assumptions. All sample size estimates below are for superiority trials, comparing a given investigational agent versus its control arm. For each trial, the specific sample size estimate and the assumptions used will be described in detail in the trial-specific appendix.

The following assumptions are used for each of the three outcomes:

- a. Treatment and control groups are of equal size (1:1 randomization).
- b. The primary analysis will by intention to treat.
- c. The type 1 error is set at 0.025 (one-sided). If several agents are investigated in parallel, each pairwise comparison of investigational agent versus placebo is considered a separate trial, and the type 1 error will not be adjusted for the number of comparisons. In specific cases, such as a trial with two or more co-primary comparisons, a type 1 error adjustment may be considered and would be described in the trial-specific appendix. Lower Type 1 error limits require higher sample sizes.

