The CRS at Day 60 (CRS-60) is an ordinal outcome that combines information about mortality and duration of recovery for those that do so (section 4.1.4). CRS-60 is defined as follows: participants who died at any time through Day 60 are in the worst category (value -2); those who are alive at Day 60 but hospitalized or receiving hospice care at Day 60 are in the secondworst category (value -1); participants who are alive, at home but not fully recovered at Day 60 are in the third-worst category (value 0; these participants are not recovered at Day 60, and thus have been recovered for 0 days). For participants who recovered (i.e., at home and fully recovered), the ordinal category is the number of days that a participant had been recovered by Day 60. The treatment difference is expressed as a summary odds ratio, comparing the odds of being in a better category for participants randomized to the investigational agent versus the placebo group. The primary analysis for the treatment comparison uses proportional odds models, with an indicator variable for the treatment effect.

The sample size required to detect a treatment difference in *CRS-60* depends on the distribution of the ordinal outcome across the many categories as well as on the hypothesized size of the treatment effect. Assuming that the proportional odds model for the treatment effect is correct, power is highest for an approximately even distribution across categories. This is typically not fulfilled, since by design probabilities of recovery on any given study day tend to be higher in early study days than towards the end of follow-up, and death forms its own

Version 1.0, 11th November 2022

US IND# 162149

category. Below we are using the distribution of the *CRS-60* ordinal outcome in the ACTIV-3 trial for tixagevimab/cilgavimab combination monoclonal antibody treatment for COVID-19, assessed at Day 60, to inform a plausible assumption for the distribution of participants across the categories of the ordinal outcome, pooled across treatment groups.

Sample size calculations used the following assumptions, in addition to assumptions a-c above:

- d. Treatment groups will be compared for CRS-60 using a proportional odds model with an indicator variable for the treatment group; the treatment effect is estimated as summary odds ratio.
- e. Power is set at 80% or 90% to detect an odds ratio of 1.20, 1.25, 1.30 and 1.35 comparing the investigational treatment versus control.

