- f. The total sample size needed to accrue the required number of events depends on the underlying distribution across the ordinal categories, pooled across treatment groups. Table 6.3 summarizes observed distributions in the ACTIV-3 trial for tixagevimab/cilgavimab. Table 6.4 summarizes the total sample size needed to detect odds ratios between 1.20 and 1.35, inflated by 5% to account for withdrawal of consent, loss to follow-up, and missing data. For example, for distributions similar to those in the trial, a total sample size of 2986 participants is sufficient order to detect rate ratio of 1.20 with 80% power.

Table 6. 3: Distribution Cross Categories of the *CRS-60* Outcome (values -2 to 60) Used to Calculate Sample Sizes in Table 6.4. For the 1397 participants with ascertained outcome out of 1417 participants in the ACTIV-3 tixagevimab/cilgavimab trial. The summary OR comparing Active versus Control for this outcome is OR=1.15 (95% CI: 0.95, 1.38), p=0.14.

Days recovered	Death (-2)	Hosp. (-1)	0	1	 57	58	59	60
Active	0.086	0.033	0.033	0.000	 0.093	0.064	0.071	0.057
Control	0.121	0.025	0.037	0.000	 0.059	0.069	0.077	0.052
Pooled	0.103	0.029	0.035	0.000	 0.076	0.067	0.074	0.054

Table 6. 4: Sample Size Needed to Detect Odds Ratios Between 1.20 and 1.35 with 80% and 90% Power. Given the distribution of days recovered through Day 60 described in Table 6.3.

	Odd	Odds Ratio (Agent versus Control)					
	OR=1.20 OR=1.25 OR=1.30 OR=1.35						
Total sample size, 80% power	2986	1994	1442	1102			
90% power	3998	2669	1931	1476			

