11.3.2.1 Early Futility Assessment

In some cases, an early futility assessment may be specified using an intermediary futility outcome. For example, in a trial where the primary outcome is an ordinal scale assessed at Day 60 (e.g., *CRS-60*), an early futility assessment could be based on time to hospital discharge, or on the 7-category ordinal outcome assessed at Day 14. This might be warranted when there is an acceptable intermediate outcome and many competing agents in the platform combined with the need to quickly identify and concentrate resources on the most promising agent(s), or when preliminary data supporting activity of the investigational agent in the trial population is lacking and thus establishing such activity is warranted to justify further resource intensive evaluation based on the primary outcome. Rationale and details regarding such an approach will be prespecified in the trial-specific appendix.

12 Protection of Human Subjects and Other Ethical Considerations

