Symptom-directed physical exam by the clinical team	Х												
Review test results for specific viral infection	Х												
Local laboratory testing	Х						Х						
Urine or serum pregnancy test or other documentation of pregnancy status for women of childbearing potential	Х												
STUDY INTERVENTION													
Randomization		Х											
Baseline signs/symptoms		Х											
Initiation of study drug/placebo administration ²		Х											
Initiation of monitoring for adverse reactions ²		Х											
Initiation of monitoring for completion of drug administration ²		Х											
STUDY PROCEDURES													
Clinical assessment for ordinal outcome		X ³	Х	Х	Х	Х	Х	Х	Х	Х	Х		Х
Hospitalization status					Х		Х		Х	Х	Х		Х
Changes in residence/facility			Х	Х	Х	Х	Х	Х	Х	Х	Х	Х	Х
Interim medical history									Х	Х	Х	Χ	Х

Version 1.0, 11th November 2022

US IND# 162149

	Screen or Day 0	Day 0	Fo	llow-	ıp Stu	idy Da	ıy: sh	aded o		ns de	note ii	n-pers	on
Day	-1/0 ¹	0	1	2	3	4	5	6	7	14	28	42	60
Acceptable deviation from day	0	0	0	0	0	0	0	+1	+6	+13	+13	+17	+20
Current medications							Х				Х		
Clinical AEs reaching grade 3 or 4 severity through Day 28 ⁴			X	Х	Х	Х	Х	Х	Х	Х	Х		
EuroQol (EQ-5D-5L)													X
SAEs and unanticipated problems				1		R	eport	as the	еу ос	cur			
AESI ⁵						R	eport	as the	еу ос	cur			
Vaccinations for source of infection						Re	port v	when	recei	ved			
PDACEs (section 4.2.3)						R	eport	as the	еу ос	cur			
Deaths			Report as they occur										
Hospitalization summary			Report upon hospital discharge										
Hospital readmissions ⁶				R	eport	ed as	a cha	ange i	n res	idence	e/facil	ity	

¹ Screening must be performed within 24 hours of randomization.

² These activities continue for length of time required to fully administer the study agent.

³ Recorded prior to randomization.

⁴ Defined for each trial – see section 10.3.1.

⁵ Defined for each trial – see section 10.2.4.

⁶ May also be reportable as an SAE

Version 1.0, 11th November 2022

US IND# 162149

Specimen Time and Events Table

This section will be completed in the trial-specific appendix based on the chosen Specimen Schedule.

	Screen or Day 0	Day 0		Foll	ow-up S	Study	Day: sh	aded	colun	nns den	ote in-pe	erson vi	sits
Day	-1/0 ¹	0	1	2	3	4	5	6	7	14	28	42	60
Acceptable deviation from day	0	0	0	0	+/-1	0	+/-1	+1	+6	+13	+13	+17	+20
Research sample storage (plasma and serum													
Airway swab for central determination of viral genome levels													

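### The 7-category ordinal outcome is recorded before randomization, but its models leave that baseline value out; where severity strata merge categories, some power on a secondary outcome is given up

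*Protocol*

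**What the plan says.** Section 4.2.2 lists the 7-category outcome as a secondary efficacy outcome on Days 1-7, 14 and 28. Category 2 is symptomatic without supplemental oxygen, 3 is under 4 L/min, 4 is 4 L/min or more short of high flow, 5 is non-invasive ventilation or high flow, and 6 is invasive or other organ support.

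Section 11.2 assigns it proportional odds models and then fixes the adjustment for this group of outcomes: "These analyses will be stratified by disease severity and study site". No baseline value is named.

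In Appendix A's Clinical Time and Events Table, the row for the ordinal assessment has a Day 0 entry with the footnote "Recorded prior to randomization".

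Section 6.2.5 leaves severity strata to each trial and gives a COVID-19 example: "1) invasive mechanical ventilation (IMV) or extra corporal membrane oxygenation (ECMO), 2) high-flow nasal cannula (HFNC) or non-invasive ventilation (NIV), 3) less than HFNC/NIV". The template in Appendix E instead uses two strata, HFNO/NIV and IMV/ECMO.

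Section 11.3.2.1 says an early futility assessment may in some cases use an intermediate outcome, for example time to discharge "or on the 7-category ordinal outcome assessed at Day 14". Rationale and details go to the trial-specific appendix.

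**The concern.** The pre-randomization value of an ordinal outcome usually carries information about its later values. Stratifying by severity recovers that information only as far as the strata separate the ordinal categories.

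Under the COVID-19 example they separate little below HFNC/NIV. Patients on no oxygen, on less than 4 L/min and on 4 L/min or more share one stratum, although the outcome treats them as three categories. Category 1 (usual activities, minimal symptoms) should be rare at entry, given the admission requirement and the exclusion of patients about to go home (Section 7.2). The merged categories are therefore in practice 2 to 4.

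By the 2020-2021 admission mix in Section 2.2.1.2, with 10-30% on high flow or above, this one stratum would hold 70-90% of patients. Within it, a baseline value that this schedule collects is not used. At stake is power on a secondary outcome, not validity.

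**Working it through.** **1. Reproducing the plan's own ordinal figures.** The only ordinal sample sizes are in Table 6.4, for CRS-60. Inputs from Sections 6.4 and 6.4.3: one-sided 0.025, 1:1 allocation, 80% or 90% power, odds ratios 1.20 to 1.35, and totals "inflated by 5% to account for withdrawal of consent, loss to follow-up, and missing data". Whitehead's formula is

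N = 12 (z₀.₉₇₅ + z_power)² / [ln(OR)² (1 − Σp³)]

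The p are the pooled shares in Table 6.3, with the unlisted mass spread over the remaining categories. For OR 1.20 at 80% power: 12 × 2.802² / [0.1823² × (1 − 0.003)] ≈ 2,842. Inflating by 5%, as × 1.05 or ÷ 0.95 and depending on how the mass is spread, gives 2,983 to 2,995 against the stated 2,986. All eight entries reproduce within 0.4%. No such figure exists for the 7-category outcome, so the 80% starting power below is an assumption.

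**2. What a given gain requires.** If the Day 0 category explains a share R² of outcome variance beyond the strata, then approximately

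power = Φ[(1.960 + z_power)/√(1 − R²) − 1.960]

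From 80% power, R² = 0.02 gives +0.8 points, 0.05 gives +2.0, 0.10 gives about +4 and 0.34 about +13. Gains of 4 to 13 points thus need a partial correlation of √0.10 = 0.32 to √0.34 = 0.58. The protocol states none.

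**3. Proportional odds fits.** Expected-likelihood fits compared treatment plus severity strata with treatment plus Day 0 category. N was set so that the strata-only model has 80% power. True OR was 1.30, and site was ignored. Assumed Day 14 distribution over categories 1 to 7: 35/30/10/5/5/7/8%. Baseline shares over categories 2 to 6 are also assumed. The mixed row stays within the ranges of Section 2.2.1.2: 25% no oxygen, 40 + 15 = 55% low flow, 12 + 8 = 20% above. The first three rows use the COVID-19 example strata. The last uses the Appendix E strata.

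Gain in power on Day 14, in points, by assumed prognostic odds ratio per baseline category:

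| Baseline mix (categories 2-6) | 1.5 | 2 | 2.5 | 3 | 4 | 6 |
|---|---|---|---|---|---|---|
| Mixed, 25/40/15/12/8% | 0.8 | 2.3 | 3.7 | 5.0 | 7.2 | 10.2 |
| Categories 2-4 only, 30/45/25% | 1.2 | 3.3 | 5.5 | 7.5 | 10.6 | 14.4 |
| Severe, 5/15/20/35/25% | 0.4 | 0.9 | 1.3 | 1.5 | 1.8 | 2.1 |
| Categories 5 and 6 only, 60/40% | 0.0 | 0.0 | 0.0 | 0.0 | 0.0 | 0.0 |

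To read one cell: 85.0% power in the mixed row at 3 means an expected Z of 1.960 + 1.036 = 2.996 against 2.802. The ratio is 1.07, worth about 1.07² − 1 = 14% more participants. From a 90% start the mixed row gains 0.6 to 6.5 points.

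**4. A rough anchor for prognosis.** Section 2.2.1.2 gives 90-day mortality of 3-5% without oxygen and 20-40% on high flow or above. The odds ratio lies between (0.20/0.80)/(0.05/0.95) = 4.75 and (0.40/0.60)/(0.03/0.97) = 21.6. Spread over three ordinal steps (category 2 to 5), the cube roots are 1.7 to 2.8 per category. This comes from mortality, not from the ordinal outcome, and says little about differences within the merged stratum. It is an indication only.

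**The case against.** The case against is substantial. Stratifying by the randomization factors is unbiased and keeps the type 1 error. The outcome is secondary, so primary power and sample size are untouched. The coarse strata are an example: a trial may define finer ones, and Section 11.2 would then adjust for them. With the Appendix E strata the gain is nil. Section 11 leaves details to trial-specific SAPs, and appendices supersede the master protocol. The admission mix describes COVID-19 in 2020-2021, not enrolled participants, and the fits omit site. All of this stands and limits the size of the point.

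One part does not carry. The protocol is not silent on adjustment: Section 11.2 names the set, which becomes the default each trial inherits. Asking for a better set is a comment on stated text. Section 11.1 already pools small sites to avoid losing power, so precision is an accepted aim.

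A reader might infer three stronger things that the documents do not support:

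- **A firm loss of 4 to 13 points.** That range needs a baseline-outcome correlation the protocol never gives, an assumed 80% start, and a population mostly below HFNC/NIV.
- **A loss in a planned Day 14 futility look, so that effective agents are dropped.** No such look is planned. Section 11.3.2.1 offers the outcome as one of two examples and fixes no model or threshold, and Section 11.3 calls its guidelines non-binding.
- **That the Day 0 category is the strongest predictor of the early days.** This is plausible, but nothing in the protocol establishes it.

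**Conclusion.** The point holds as a low-cost improvement to a valid analysis. Section 11.2 specifies an adjustment set that leaves out a baseline value which the maximal schedule collects before randomization. Some power is lost wherever severity strata merge ordinal categories.

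The Day 14 loss is about 0 to 14 points, assuming 80% power for the strata-only model, a true odds ratio of 1.30 and the assumed distributions above. It is 0 when strata match the categories and 0.4 to 2.1 in a severe mix. In a mixed population it is about 1 to 5 for a prognostic odds ratio per category of 1.5 to 3. It reaches 10 or more only with strong prognosis: 4 or above when only categories 2-4 are enrolled, 6 in the mixed case. Any consequence for futility is conditional on a trial appendix adopting this outcome for that purpose.

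**What to change.** In Section 11.2, state that the proportional odds models for the 7-category outcome on each analysis day also include the Day 0 ordinal category as a categorical covariate. Keep the stratification by site and disease severity, and omit the covariate where it is redundant with the severity strata. Add to Section 11.3.2.1 that a trial appendix adopting the Day 14 ordinal outcome for early futility uses the same adjusted model.

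The cost is a few degrees of freedom. With five baseline categories nested in three strata it is 5 − 3 = 2 extra parameters, slightly more where categories and strata do not nest exactly. No new data, visit or sample size is needed for trials on this schedule. A trial using a reduced schedule must keep the Day 0 assessment. The reported odds ratio becomes conditional on the Day 0 category and should be labelled so.

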11.3 Data Monitoring Guidelines for an Independent DSMB

An independent data and safety monitoring board (DSMB) will review all trials conducted in the STRIVE platform. Each individual trial will be reviewed at least twice a year and may be reviewed more frequently as needed. These full DSMB reviews include the general trial conduct as well as extensive data summaries of the primary outcome and other major clinical outcomes.

In addition to the full reviews, interim safety reviews by the DSMB may be scheduled more frequently. In particular, for investigational agents with limited safety data, an early safety review with 20-30 participants will be included, followed by frequent interim safety reviews. The monitoring plan for safety, efficacy and futility is described below. If a modification of the monitoring plan is needed for an individual trial, it will be pre-specified in the trial-specific protocol appendix and statistical analysis plan.

The monitoring guidelines for the DSMB described in this section are guidelines, not binding rules. The DSMB is expected to use their independent judgment in determining whether a trial should be terminated or modified, based on comprehensive reviews of data from the current trial and available external data since there are many considerations in determining whether a trial should be stopped early.

The DSMB will be asked to recommend early termination of a trial for efficacy only when there is clear and substantial evidence of a treatment difference. Conversely, the DSMB may recommend discontinuation of an investigational agent if the risks are judged to outweigh the benefits, or if pre-specified futility assessments indicate that there is low probability that the investigational agent will achieve statistical significance for the primary outcome. In addition to the unblinded data summaries, the DSMB will also review other relevant data that might impact the trial design, e.g., emerging data from other trials.

When several agents are investigated in parallel with a shared control group, each agent will be compared to its corresponding contemporaneously randomized pooled placebo group. Each investigational agent versus control comparison will be treated as a separate trial; the DSMB may recommend stopping one arm of the trial but continuing others. Stopping boundaries will be adjusted for multiple looks, but will not be additionally inflated to adjust for simultaneous analyses of multiple agents, except when explicitly stated in the trial-specific appendix and statistical analysis plan.

